6.0 Statistical Analysis Plan

The study is designed to evaluate the effects of MDC on patient activation (primary analysis) and explore the effects on other secondary cognitive and behavioral outcomes relative to the control group. We will use a t-test to compare the change in PAM score between the MDC and control groups. If the normality assumption is violated, the non-parametric Wilcoxon rank sum test will be used. We will use mixed-effects regression models to estimate the intervention effects across time while adjusting for the baseline measure of the outcome. Nonlinear associations will be modeled with regression splines. The mixed-effects model will use fixed effects for patient-level characteristics and random effects for health care provider variables. We will provide point estimates with CIs and graphically depict our results. If necessary, multiple imputation will be used to impute the missing values. The analysis with multiple imputation assumes missing at random (i.e., the model properly handles missing data by including covariates associated with reasons for dropout). The characteristics of participants who do not complete the study or do not comply with the treatment will be compared for both

conditions. Independent t-tests or if appropriate, Wilcoxon rank sum tests will be used to compare change in secondary outcomes between the MCD and control groups. Mixed-effect models will also be used to evaluate the effects of MDC on secondary outcomes across time.

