4.0 Enrollment/Randomization

Participants will be able to complete an electronic consent form and enroll online via Research Electronic Data Capture (REDCap™) version 5.0.8. The study coordinator will verify all eligibility criteria prior to randomization. The procedure and risks will be explained to the participants and the consent form signed as per standard practice. All participants are randomly assigned to one of two groups: (1) intervention group which will have access to a version of MHAV embedded with the MDC or (2) usual care group which will have access to the currently available version of MHAV. Participants randomized to the intervention are advised to view MDC on a desktop or laptop device because the present version of MDC is not mobile friendly. The randomization sequence will be generated by the research team biostatistician using a permuted block randomization scheme stratified by clinic site and participants' age group (age 65 and over vs under 65). The randomized assignment for eligible participants will be accessible to the study coordinator and biostatistician using the Research Electronic Data Capture (REDCap™) Randomization Module. Once a randomization assignment is provided, the participant will be entered into the study and will be included in an intention to treat analysis in accordance with the CONSORT guidelines. Our target enrollment is 300 participants (150 per arm).

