5.0 Study Procedures

Setting. Participants will be recruited from 14 VUMC-affiliate adult primary care clinics located throughout Middle Tennessee (4 urban, 10 suburban). An EHR (Epic Systems Corp.) stores all clinical data and patients receive access to their clinical data via an integrated and highly-adopted patient web portal, MHAV.

Participants and Recruitment. On a rolling basis, potentially eligible patients will be selected from a randomly ordered list of established adult patients with diabetes from participating clinic sites and sent a recruitment letter describing the study. In addition, we will use My Research at Vanderbilt to send the recruitment letter to current patient portal users who elected to allow investigators to contact them about research opportunities via email. Interested patients can contact a research assistant to learn more about the study. To enroll, participants will complete a web-based study eligibility screener and electronic consent form on the web via REDCap (Research Electronic Data Capture) version 5.0.8.

Intervention and Control. Participants randomized to the intervention arm will be provided access to a version of MHAV embedded with the MDC viewable on a desktop or laptop device (MDC is not currently available on mobile devices). MDC includes infographics to visualize and summarize patients' health data, incorporates motivational strategies (e.g., social comparisons and gamification), provides literacy-level appropriate educational resources, and contains secure-messaging capability. Participants randomized to the usual care arm will have access to the currently available version of MHAV that includes the ability for patients to review pertinent health data, review medical information about their conditions, and communicate with their health care team.

Data Collection and Outcome Measures. Study participants will complete questionnaires electronically via email using REDCap™ at three time points: enrollment (T_0), three-month follow-up (T_1), and six-month follow-up (T_2). Enrolled participants will be asked to provide information on the following covariates: socioeconomic status, marital status, race/ethnicity, education level, and health literacy.

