The primary outcome measure will be change in patient activation as assessed by the Patient Activation Measure (PAM-13). Secondary intermediate outcomes include diabetes self-efficacy, diabetes knowledge, diabetes distress, diabetes self-care, system usability/satisfaction, and system usage. Additional secondary outcome such as blood glucose control, blood pressure control, cholesterol control, and flu vaccination status will also be assessed by EHR abstraction. To ensure the fidelity of the intervention, monthly quality assurance checks will be used to ensure the MDC is functioning correctly (e.g., displaying data correctly).

Based on pilot testing, we estimate time to completion for questionnaires to be about 25 minutes at T_0 and about 20 minutes at T_1 and T_2 . Participants will be compensated \$40 for completing the enrollment questionnaire (T_0) and \$35 each for completing the three-month (T_1) and six-month (T_2) follow-up questionnaires.

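### The primary comparison of PAM change reads as an unadjusted t-test, and the planned baseline-adjusted mixed model is given no rank

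*Combined protocol and SAP*

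**What the plan says.** - Section 5.0 (Study Procedures) defines the outcome as a change: "The primary outcome measure will be change in patient activation as assessed by the Patient Activation Measure (PAM-13"). PAM is collected at enrolment (T0), three months (T1) and six months (T2). The section does not say which follow-up the change refers to.
- Section 6.0 attaches the primary label to the objective: "The study is designed to evaluate the effects of MDC on patient activation (primary analysis"). The sentence after that reads "We will use a t-test to compare the change in PAM score between the MDC and control groups", with an unadjusted Wilcoxon rank sum test as fallback if normality fails.
- The same section then adds "We will use mixed-effects regression models to estimate the intervention effects across time while adjusting for the baseline measure of the outcome", and specifies "The mixed-effects model will use fixed effects for patient-level characteristics and random effects for health care provider variables". It does not call this model primary, secondary, supportive or a sensitivity analysis.
- For secondary outcomes, t-tests or Wilcoxon tests come first, and then "Mixed-effect models will also be used to evaluate the effects of MDC on secondary outcomes across time".
- Section 4.0 (Enrollment/Randomization) describes a "permuted block randomization scheme stratified by clinic site" and by age group (65 and over versus under 65). The t-test uses neither factor, and neither is named in the mixed-model text.

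**The concern.** Two analyses of one primary outcome are planned and neither is ranked. The order of the sentences, and an outcome defined as change, point to the t-test as the primary comparison and the mixed model as an addition.

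On that reading the main question is answered by the less efficient of the two planned methods. A change score subtracts baseline with a coefficient of exactly 1, whereas a baseline-adjusted analysis estimates the coefficient. The two agree in large-sample precision only when the true coefficient happens to be 1. Otherwise the t-test has lower power and a wider interval than the T0 data allow. If the t-test and the mixed model disagreed, nothing in the plan would say which result counts.

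This is a matter of efficiency and ranking. The t-test is unbiased under randomisation, so validity is not in question.

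**Working it through.** **Inputs from the documents.** 300 participants, 150 per arm; 14 clinics; two age groups; PAM at T0, T1 and T2 (Sections 3.0 to 5.0). The target of 300 cannot be reproduced, because no alpha, power, effect size, SD or dropout rate is given.

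**Assumptions.** Correlation ρ between baseline and follow-up PAM of 0.3 to 0.9; two-sided 5% test; 80% power for illustration, so the multiplier is 1.960 + 0.842 = 2.802; no dropout.

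**Equal SDs (s), one follow-up time.**

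- Change score: variance 2s²(1 − ρ)
- Baseline-adjusted: variance s²(1 − ρ²)
- Ratio, adjusted to change: (1 + ρ)/2, so the information lost is (1 − ρ)/2
- Relative CI width of the t-test: 1/√ratio
- Power after adjustment when the t-test has 80%: Φ(2.802/√ratio − 1.960)
- Detectable difference in SD units: 2.802 × √(2V/150), where V is the variance above with s = 1. At ρ = 0.3 the t-test gives 2.802 × √(2.8/150) = 0.383 and adjustment gives 2.802 × √(1.82/150) = 0.309.

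| ρ | Ratio | Information lost | t-test CI wider by | Power after adjustment | Detectable, t-test | Detectable, adjusted |
|---|---|---|---|---|---|---|
| 0.3 | 0.65 | 35% | 24% | 93.5% | 0.383 SD | 0.309 SD |
| 0.5 | 0.75 | 25% | 15% | 89.9% | 0.323 SD | 0.280 SD |
| 0.7 | 0.85 | 15% | 8% | 86.0% | 0.251 SD | 0.231 SD |
| 0.9 | 0.95 | 5% | 3% | 82.0% | 0.145 SD | 0.141 SD |

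Simulated variance ratios (6,000 trials per ρ) were 0.667, 0.745, 0.857 and 0.947, close to the formula.

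**Other cases.** With k the ratio of follow-up to baseline SD, the variance ratio is k²(1 − ρ²)/(k² + 1 − 2ρk). If change means the T1/T2 average minus T0, with equal SDs and all correlations ρ, the variances are 1.5(1 − ρ) and (1 − ρ)(1 + 2ρ)/2. The ratio is then (1 + 2ρ)/3 and the loss 2(1 − ρ)/3.

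| Information lost at ρ = | 0.3 | 0.5 | 0.7 | 0.9 |
|---|---|---|---|---|
| k = 0.9 | 42% | 33% | 25% | 19% |
| k = 1.2 | 24% | 13% | 3% | 2% |
| T1/T2 average | 47% | 33% | 20% | 7% |

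With one follow-up time, the loss is zero when ρk = 1.

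**Cost of adding the strata.** A simulation used 300 participants, 14 clinics by 2 age groups, blocks of 4 (block size assumed) and no true clinic or age effect. Power at ρ = 0.3, 0.5, 0.7 and 0.9 was:

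- change t-test: 0.791, 0.796, 0.795, 0.795
- baseline only: 0.931, 0.894, 0.852, 0.815
- baseline, age group and clinic (fixed): 0.929, 0.893, 0.850, 0.817

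The strata cost almost nothing even when they predict nothing.

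**Does the gain carry over to a mixed model?** In 60 simulated complete-data trials (ρ = 0.5, 150 per arm), a mixed model over T1 and T2 with treatment by time, baseline by time and a random intercept gave the same T2 estimate as analysis of covariance at T2 (difference below 1e-14). Mean standard errors were 0.0998 (mixed), 0.1001 (covariance) and 0.1159 (change t-test).

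**The case against.** The strongest reply is that the adjustment is already in the plan. The primary label belongs to the objective, not to the t-test. The word *also* in the secondary-outcome sentence may only extend the PAM mixed models to the other outcomes. The promise of estimates with confidence intervals follows the mixed-model text, so the reported intervals may be baseline-adjusted, leaving only the t-test's p-value less efficient. All this is possible, and it is why the plan can only be said to *read as* making the t-test primary. It does not supply a rank: under each reading the plan still leaves open which result decides.

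A second reply is that the loss is unknown. That stands. The documents give no correlation or SD, the assumed range has no source in them, and the calculated losses run from 2% to 47%. Most of the figures also describe a single-timepoint analysis without dropout, not the full planned model with splines, provider effects and imputation. They support a range, not a single figure.

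Third, no loss from omitting the strata has been shown, and age may already be among the patient-level characteristics. That also stands; the simulation shows only that including the strata is nearly free.

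Finally, a simple test of change is a legitimate choice in a study that Section 2.0 calls a pilot. True, and it limits the weight of the point. But the study names a primary outcome and randomises 300 people to evaluate it, and the more efficient analysis is already planned.

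**Conclusion.** The concern holds as a point of efficiency and pre-specification that should be addressed. Section 6.0 does not rank its two PAM analyses, and its natural reading favours the less precise one. With equal SDs and one follow-up time, the precision forgone is material at low or moderate correlation (35% of the information at 0.3, 25% at 0.5) and trivial near 0.9 (5%). These sizes rest on the assumed correlations and SD ratios, a two-sided 5% level and no dropout, and they apply to the t-test, not to the Wilcoxon fallback. If the sponsor intended the mixed model as primary, there is no loss of precision and the gap is one of wording.

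**What to change.** State in Section 6.0 that the baseline-adjusted model is primary. Possible wording:

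> The primary analysis is a mixed model of PAM at T1 and T2 with treatment, time, treatment by time, baseline PAM, baseline PAM by time, age group (65 and over vs under 65) and clinic site as fixed effects, and a participant random effect. The primary estimate is the adjusted mean difference at [timepoint named by the sponsor] with its 95% CI. The change-score t-test or Wilcoxon test is supportive.

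The essential parts are the rank, baseline PAM, the strata and the timepoint; the rest of the form is the sponsor's choice. If provider random effects are kept, the text should say so. Clinic may be random instead of fixed if that is stated in advance. A linear model of PAM at the named timepoint with the same covariates is an acceptable alternative; with complete data, and every covariate interacting with time in the mixed model, the two give the same treatment estimate. The outcome can still be called change, because with baseline PAM as a covariate, modelling change or follow-up PAM gives the same treatment estimate.

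The cost is SAP wording, including the choice of timepoint. Baseline PAM, clinic and age group are already collected. The small downside is reliance on a regression model in place of a simple test.

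### Despite the intention-to-treat promise, the primary t-test on PAM change by default leaves out people without follow-up; imputation has no trigger, and the planned mixed model is not designated primary

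*Combined protocol and SAP*

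**What the plan says.** Section 4.0 states that once assigned, a participant "will be included in an intention to treat analysis in accordance with the CONSORT guidelines".

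Section 5.0 defines the endpoint: "The primary outcome measure will be change in patient activation as assessed by the Patient Activation Measure (PAM-13"). It does not say whether the change is to three months (T1) or six months (T2). On collection it says: "Study participants will complete questionnaires electronically via email using REDCap™ at three time points". A participant who does not answer therefore has no PAM score at that visit.

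Section 6.0 labels patient activation the primary analysis and then gives the test: "We will use a t-test to compare the change in PAM score between the MDC and control groups". The fallback is "If the normality assumption is violated, the non-parametric Wilcoxon rank sum test will be used". Next come mixed-effects models for the effect over time, adjusted for the baseline value. Missing data are covered by "If necessary, multiple imputation will be used to impute the missing values" and "The analysis with multiple imputation assumes missing at random". The section also plans to compare the characteristics of non-completers in the two arms.

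**The concern.** A t-test or rank-sum test on change needs a change score for each person, so someone with no follow-up PAM drops out of it unless a value is imputed. The plan does not say when imputation becomes necessary, which variables it uses, or whether it feeds the primary test. The safeguards that are present are not tied to the primary result: the mixed model has no precedence over the t-test if the two disagree, and the comparison of non-completers has no stated consequence.

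The promise to analyse everyone randomised is thus only partly carried out. If people who leave one arm differ in outcome from those who leave the other, a completer comparison can create an effect or hide one. Section 2.0 calls the study a pilot for a larger definitive trial, so a distorted estimate could carry into that decision.

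**Working it through.** **Inputs from the documents.** 150 per arm (section 4.0); PAM at T0, T1 and T2 (section 5.0); a t-test on change (section 6.0). The plan gives no alpha, effect size, SD, power or dropout rate, so its 300 cannot be reproduced. For reference, with an assumed two-sided 5% test and 80% power, 150 per arm matches a standardised difference of 0.324: 2 × (1.960 + 0.842)² / 0.324² = 15.70 / 0.105 ≈ 150. Everything below on dropout is assumption.

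**Step 1: bias of a completer comparison.** Let d be the share lost in an arm and g the mean change of completers minus that of dropouts, in SDs of change. The completer mean exceeds the full-arm mean by d × g, so

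bias = d(MDC) × g(MDC) − d(UC) × g(UC), with SE = √(1/n(MDC) + 1/n(UC)).

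The false-positive rate is Φ(bias/SE − 1.96) + Φ(−bias/SE − 1.96).

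Worked case: loss 20% and 10%, gap 0.5 SD in MDC and none in usual care. The numbers left are 120 and 135, so SE = 0.1255. Bias = 0.20 × 0.5 − 0 = 0.10, bias/SE = 0.80, and the rate is 12.5%.

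| Loss MDC / UC | Gap MDC / UC (SD) | Bias (SD) | False-positive rate |
|---|---|---|---|
| 20% / 20% | 0.5 / 0.5 | 0 | 5% |
| 20% / 10% | 0.5 / 0.5 | 0.05 | 6.8% |
| 10% / 10% | 0.5 / 0 | 0.05 | 7% |
| 20% / 10% | 0.5 / 0 | 0.10 | 12.5% |
| 20% / 10% | 1.0 / 0 | 0.20 | 36% |

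Bias is zero when rate and gap are the same in both arms. A difference in either one is enough to bring it back.

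**Step 2: hiding an effect.** With a true effect of 0.324 SD and 20%/10% loss, power without bias is 73%. With bias −0.10, (0.324 − 0.10)/0.1255 = 1.785 and power is Φ(1.785 − 1.960) = 43%. With bias −0.20 it is 17%.

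**Step 3: what the T1 score recovers.** Simulation under no true effect, T2 taken as the primary visit: 150 per arm; PAM correlations 0.60 (T0-T1), 0.55 (T0-T2), 0.70 (T1-T2); T1 seen for everyone; 20% of T2 lost in each arm. Loss is random in usual care. In MDC it depends on T1−T0 improvement, with log-odds −0.5 or −1.0 per SD. Bias is in SDs of the PAM score.

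| Analysis | Bias, slope −0.5 / −1.0 | False-positive rate |
|---|---|---|
| Completer t-test on change | 0.063 / 0.106 | 8.0% / 14.1% |
| Completer ANCOVA on T0 | not tabulated | 6.7% / 9.8% |
| Likelihood estimate, T0 and T1 from all | 0.003 / 0.001 | 4.7% / 4.6% |

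Repeat runs gave 7-14% for the t-test and about 5% for the likelihood estimate. With the same loss mechanism in both arms the t-test stayed at about 5%; with usual care at half the MDC slope it was 6.0% / 6.6%. With a true 0.3 SD effect and loss running the opposite way in MDC, power fell to 36% for the t-test against 82% for the likelihood estimate.

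**Step 4: power when loss is harmless.** For 0.324 SD, equal random loss of 10%, 20% and 30% lowers t-test power from 80% to 76%, 71% and 65%. In the simulation with 20% random loss and a 0.3 SD effect, power was 68% for the t-test and 81% for the likelihood estimate, most of the gain coming from baseline adjustment.

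**Step 5: limits of the remedy.** A separate simulation assumed no true effect, 20%/10% loss, random loss in usual care and correlations 0.6/0.6/0.7. When MDC loss depended on the observed T1 change, the completer t-test had bias 0.15 SD and 23% false positives; multiple imputation by arm had 0.00 SD and 5%. When loss depended on the unseen T2 change, the figures were 0.23 SD and 50% against 0.14 SD and 23%. Imputation under missing at random removes the first problem and only part of the second. If the same dropouts also give no T1 score, only T0 is left to condition on, and rejection in the Step 3 setting was 6.0% / 10.6%.

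**The case against.** The plan does address missing data. Its mixed model is close to the remedy and would use a T1 score from someone missing T2; it names multiple imputation and its assumption; and it will compare non-completers. This stands. A reader might infer that missing data are ignored or that the intention-to-treat promise is contradicted, and the text supports neither. The promise is incompletely implemented.

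A reader might also infer that completers-only is the plan's rule. No sentence says so. It is what these tests do unless imputation is invoked, and the conditional wording can fairly be read as imputing whenever values are missing. Nor do the documents say when that decision is taken, so they do not establish that it follows sight of unblinded data.

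The loss pattern is speculative. Both arms are paid the same for each follow-up questionnaire (section 5.0), and both are told that the study concerns satisfaction with two portal versions (section 2.0), which may weaken any link between perceived benefit and response. The simulation's MDC-only mechanism favours the concern, and its T2 endpoint is not stated in the plan. If T1 is primary, there is no earlier follow-up PAM score to draw on and the near-zero bias in Step 3 does not apply.

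What survives is narrower: the analysis that handles partial follow-up is not the primary one, and imputation is not committed to the one that is.

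**Conclusion.** The point holds as an avoidable weakness in the primary analysis. That the primary test has no assured treatment of missing follow-up is clear from sections 4.0 and 6.0. The size of any bias is conditional and cannot be computed for this trial, because the documents give no dropout figure.

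Under the assumed 20% loss, informative in the MDC arm only, with T2 primary and T1 complete, type I error is about 7-14% for the completer t-test and about 5% for the likelihood analysis. Loss in the other direction can hide an effect. Loss that is alike in both arms in rate and in relation to outcome gives no bias and costs only power. The tempting conclusion that the trial's result will be biased is not supported; that the plan leaves it exposed to such bias is. The change is worth making before outcome data are examined.

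**What to change.** Amend section 6.0 as follows.

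- **Primary analysis.** Designate the planned longitudinal mixed model as primary: baseline PAM, arm, visit and arm-by-visit, all available T1 and T2 scores, participants in their assigned arm. Name one visit at which the arm contrast is the primary estimate. State how correlation within a participant is modelled, since the section names random effects only for provider variables and the T1 score informs a missing T2 only through that correlation.
- **If a single-visit test is kept.** Always do multiple imputation, separately by arm, using T0 PAM, any other observed PAM score and the T0 covariates. People with no follow-up are then included; for them the imputation rests on baseline data alone.
- **Sensitivity analyses.** Keep the completer t-test in this role, and add a delta-adjusted analysis for loss that is not at random.

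This replaces the conditional imputation sentence. It needs no new data and no more participants. The downside is slightly more analysis work and a headline result that comes from a model instead of a simple t-test.
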